3.2 Rationale of study design

This is a mechanistic study to investigate the effect of percentage carbohydrate in the breakfast meal on the LIK066-induced diarrhea and potential treatments with a supplement in overweight or obese subjects. The study will use a randomized, open-label, two-part, three-period, cross-over design in each part of the study.

- An open label design is considered appropriate because all the primary and secondary endpoints assessed in this study are objective measures in nature. A crossover design is ideal as comparisons among treatment groups are based on within-subject differences which are associated with less variability than between-subject differences. The main objective is to assess whether or not the diarrhea adverse event can be alleviated by reducing or removing carbohydrate containing glucose and galactose in the meal or by concomitant administration of supplements, therefore, placebo control is not needed.
- The design of two parts (Part A and Part B) with 3 treatment periods, cross-over design is preferred because a single part, six treatment periods cross-over design requires longer duration of domiciling which may lead to operational complexity such as difficulty in recruitment and higher drop-out rates. The two parts, three periods design is also preferred from statistical perspective because it yields the most statistically efficient design for addressing the clinical questions.
- A five day washout period is considered sufficient based on the fact that limited diarrhea episodes were observed on the following day after the last dose of 50 mg qd (one out of 40 patients showed diarrhea on day 15 after 14 day dosing in LIK066X2201).
- A standardized breakfast meal (together with menu options for lunch and dinner) enables each subject to choose the diets following their usual eating habits during the run-in will normalize the bowel movement habit of each subject under similar meal conditions for the purpose of comparison during the treatment periods.
- The overweight or obese subjects in this study will closely represent the patient population for LIK066, which is being developed as a pharmacotherapy for obesity.

Therefore, the study design is considered adequate and appropriate to address the primary objectives, the stool consistency and incidence of diarrhea associated with LIK066 treatment, which are endpoints that can be measured objectively.

3.4 Rationale for choice of comparator

Not applicable.

3.5 Purpose and timing of interim analyses/design adaptations

An interim analysis is not planned, but may be conducted before all subjects complete the study if deemed necessary. Depending on the progress of the trial, the analysis may be conducted to support decision making concerning the current clinical study, the sponsor's clinical development strategy in general, or in case of any safety concerns.

3.6 Risks and benefits

There is no anticipated therapeutic benefit expected for subjects participating in this study. The risk to participants in this trial will be minimized by adherence to the inclusion/exclusion criteria, close clinical monitoring during the treatment periods, and stopping rules outlined in [Section 7.5](#).

Risks of LIK066 administration in human subjects may include the development of gastrointestinal adverse reactions, postural hypotension due to volume depletion, ketoacidosis, urinary tract infection, genitourinary infection, renal and hepatic toxicity, and changes in calcium homeostasis with subsequent effects on bones, hyperglycemia and hypoglycemia.

Doses of LIK066 proposed in this study have been tested and deemed safe in healthy subjects, patients with T2DM and obese patients. Subjects should be closely monitored and treated according to the standard of care if deemed necessary by the principle investigator. LIK066 is considered an aneugen at extremely high doses. With the doses and treatment duration proposed in this study, more than 10-fold exposure multiple is maintained relative to the threshold NOEL exposure for aneugenicity. LIK066 is not anticipated to increase the risk of adverse developmental or reproductive outcomes in humans when administered at the highest planned clinical dose of 150 mg. Women of child bearing potential should be informed that taking the study drug may involve unknown risks to the fetus if pregnancy were to occur during the study and agree that in order to participate in the study they must adhere to the contraception requirement for the duration of the study ([Section 4.2](#)). If there is any question that the subject will not reliably comply, they should not be entered in the study.

The supplements used in this study are generally well tolerated and widely used as the OTC supplements. Potential risks associated with psyllium are bloating and flatulence, and those associated with calcium carbonate are constipation, gas and burping.

Blood samples will be collected frequently during the study either via venipuncture or cannula. Additional samples for monitoring of any safety findings would be in addition to this. This is not considered to be a risk for this population. Risks associated with blood collection include pain, swelling and/or bruising at the insertion site of the needle. Although rare, localized clot formation, infections and nerve damage may occur. Lightheadedness and/or fainting may also occur during or shortly after the blood draw.

There may be unknown risks to LIK066 which may be serious and unforeseen.

3.6.1 Blood sample volumes

Approximately 450 mL of blood is planned to be collected over a period of 8 weeks including the Screening visit, from each subject as part of the study. Additional samples for monitoring of any safety findings would be in addition to this. This is not considered to be a risk for this population.

Timings of blood sample collection are outlined in the Assessment Schedule, [Section 8.1](#).

A summary blood log is provided in the Site Operations Manual, together with instructions for all sample collection, processing, storage, and shipment information.

See [Section 8.9](#) regarding the potential use of residual samples.

4 Population

The study population will consist of male and female overweight or obese subjects.

A total of approximately 48 patients will be enrolled in the study and randomized. At least 36 subjects are expected to complete the study.

The investigator must ensure that all subjects meet the subsequent eligibility criteria at screening. No additional criteria should be applied by the investigator to ensure that the study population is representative of all eligible subjects. A relevant record (e.g. checklist) of the eligibility criteria must be stored with the documentation at the study site.

Deviation from any entry criterion excludes a patient from enrollment into the study.

4.1 Inclusion criteria

Overweight or Obese Subjects eligible for inclusion in this study must fulfill **all** of the following criteria:

1. Written informed consent must be obtained before any assessment is performed.
2. Male and female subjects age 18 to 65 years, with stable health condition as determined by past medical history, physical examination, electrocardiogram, and laboratory tests at screening.
3. Subjects with a body mass index (BMI) of 25 - 50 kg/m² at screening
4. HbA_{1c} < 10% at screening. If treated with antidiabetic medications (other than prohibited medications), subjects must be on a stable dose for 12 weeks prior to randomization and maintain the dose until the end of the study.
5. Able to communicate well with the Investigator, to understand and comply with the requirements of the study.

6. At screening and baseline, vital signs (systolic and diastolic blood pressure and pulse rate) will be assessed in the sitting position after the subject has rested for at least three (3) minutes, and again when required after three (3) minutes in the standing position

Investigators can be guided by the following ranges:

oral body temperature between 35.0-37.5 °C
sitting systolic blood pressure, 90-139 mm Hg
sitting diastolic blood pressure, 50-89 mm Hg
sitting pulse rate, 40 - 90 bpm

If vital signs are out-of-range, the Investigator may obtain two additional readings, so that up to three (3) consecutive assessments are made, each after at least 30 minutes (one hour is recommended), and with the subject seated quietly during the five (5) minutes preceding the assessment. ***At least the last reading must be within the ranges provided above in order for the subject to qualify.***

When blood pressure and pulse will be taken again after 3 minutes standing, there shall be no more than a 20 mm Hg drop in systolic or 10 mm Hg drop in diastolic blood pressure and increase in heart rate (>20 bpm) associated with clinical manifestation of postural hypotension.

All blood pressure measurements at other time-points should be assessed with the subject seated, unless stated otherwise in the protocol design, and utilizing the same arm for each determination.

4.2 Exclusion criteria

Overweight or Obese Subjects fulfilling any of the following criteria are not eligible for inclusion in this study:

1. Pre-existing, clinically significant gastrointestinal, liver, cardiovascular, renal (including familial glucosuria) or other chronic medical condition which is considered serious or unstable, other than stable cardiovascular disease, stable adequately treated hypertension, dyslipidemia or other stable chronic disorders
2. Clinically significant GI disorder related to malabsorption or that may affect drug or glucose absorption (e.g. swallowing disorder, severe GI motility disorder, chronic diarrhea, glucose/galactose/lactose intolerance)
3. History of significant gastrointestinal surgery that could affect intestinal glucose absorption (e.g. bariatric surgeries including, Roux en Y gastric bypass, sleeve gastrectomy, Nissen fundoplication)
4. History of hypersensitivity to the study drugs, or to drugs of similar chemical classes.
5. Pregnant or nursing (lactating) women, where pregnancy is defined as the state of a female after conception and until the termination of gestation, confirmed by a positive hCG laboratory test
6. Women of child-bearing potential, defined as all women physiologically capable of becoming pregnant, unless they are using basic methods of contraception during dosing of study treatment.

Basic contraception methods include:

- Total abstinence (when this is in line with the preferred and usual lifestyle of the subject. Periodic abstinence (e.g., calendar, ovulation, symptothermal, post-ovulation methods) and withdrawal are not acceptable methods of contraception.
- Female sterilization (have had surgical bilateral oophorectomy with or without hysterectomy) or tubal ligation (hysterectomy is acceptable) at least six weeks before taking study treatment. In case of oophorectomy alone, only when the reproductive status of the woman has been confirmed by follow up hormone level assessment.
- Male sterilization (at least 6 months prior to screening). For female subjects on the study, the vasectomized male partner should be the sole partner for that subject.
- Barrier methods of contraception: Condom or Occlusive cap (diaphragm or cervical/vault caps) with spermicidal foam/gel/film/cream/ vaginal suppository.
- Use of oral, injected or implanted hormonal methods of contraception or other forms of hormonal contraception that have comparable efficacy (failure rate <1%), for example hormone vaginal ring or transdermal hormone contraception.
- Placement of an intrauterine device (IUD) or intrauterine system (IUS).
- In case of use of oral contraception women should have been stable on the same pill for a minimum of 3 months before taking study treatment.

Women are considered post-menopausal and not of child bearing potential if they have had 12 months of natural (spontaneous) amenorrhea with an appropriate clinical profile (e.g. age appropriate, history of vasomotor symptoms) or have had surgical bilateral oophorectomy (with or without hysterectomy) or tubal ligation (hysterectomy is acceptable) at least six weeks ago. In the case of oophorectomy alone, only when the reproductive status of the woman has been confirmed by follow up hormone level assessment is she considered not of child bearing potential

7. Patients with type 1 diabetes, or history of acute diabetic complications such as ketoacidosis or hyperosmolar state (coma) within the 6 months prior to screening
8. Evidence of significant diabetic complications such as symptomatic neuropathy, severe diabetic retinopathy, diabetic nephropathy, diabetic gastroparesis or enteropathy
9. Use of prohibited medications, refer to [Section 5.2](#).
10. Evidence of clinically significant renal or liver disease/injury including:
 - eGFR less than 60 mL/min/1.73m² at screening.
 - Patients with macroalbuminuria as determined by spot urine albumin:creatinine ratio >300 mg/g at screening.

Abnormal liver function tests at screening:

- ALT, AST, GGT, alkaline phosphatase > 2 x ULN.
- serum bilirubin > 1.5 x ULN
11. Evidence of urinary obstruction or difficulty in voiding at screening
12. Symptomatic genital or urinary tract infection in the 4 weeks prior to first study visit
13. Any uncontrolled endocrinopathy including thyroid disease. Patients with an underlying endocrinopathy should be on stable treatment for 3 months prior to screening
14. Evidence or medical history of clinically significant ECG abnormalities

15. Any of the following within 6 months of screening:
 - Acute coronary syndrome (ACS)
 - coronary artery bypass surgery, balloon angioplasty, coronary stent(s) *in situ*
 - peripheral arterial disease
 - congestive heart failure NYHA class I- IV
16. History of autonomic dysfunction (e.g. history of fainting, clinically significant orthostatic hypotension, clinically significant sinus arrhythmia).
17. Significant blood loss equaling at least one unit of blood (500 ml) or a blood transfusion within 3 months prior to screening
18. Evidence of immunodeficiency diseases, including a positive HIV (ELISA and Western blot) test at screening
19. History of drug or alcohol abuse within the 12 months prior to initial dosing or evidence of such abuse as indicated by the laboratory assays conducted during the screening or tests conducted during baseline evaluations
20. Malignancy including leukemia and lymphoma (not including basal cell skin cancer) within 5 years prior to screening
21. Any finding during screening assessments (physical examination, vital signs, or clinical lab assessments), surgical or medical condition which might significantly alter the absorption, distribution, metabolism, or excretion of drugs, or which may jeopardize the subject, in the investigator's judgment, in case of participation in the study.
22. Subjects who experienced ketoacidosis, lactic acidosis, or hyperosmolar coma within 6 months of Screening Visit, or between Screening Visit and Baseline Day -1.
No additional exclusions may be applied by the investigator, in order to ensure that the study population will be representative of all eligible subjects.

5 Restrictions for Study Subjects

[figure not shown]
During recruitment, screening/informed consent review, and baseline visit, the subjects must be informed and reminded of the restrictions outlined in this section.

5.1 Contraception requirements

Please refer to exclusion criteria ([Section 4.2](#)) for details of contraception requirements for the study.

5.2 Prohibited treatment

Except for medication which may be required to treat adverse events, no medication including OTCs other than study drugs will be allowed from the first dosing until all of the Study Completion evaluations have been conducted. If needed, acetaminophen or ibuprofen is acceptable for incidental and limited use. Aspirin, antihypertensive, dyslipidemia, COPD and GERD medications including PPIs are allowed but subjects must be on a stable regimen for 12 weeks or more prior to randomization ([Section 6.10](#)).

The following medications are prohibited during the study:

- Antidiabetic drugs including injectable antidiabetic medications (such as insulin and GLP-1 agonists), SGLT and alpha-glucosidase inhibitors are NOT allowed during the study. Patients must be on a stable regimen for approximately 12 weeks prior to randomization if treated with other oral antidiabetic medications.
- Treatment with drugs that affect gastric motility (e.g. erythromycin)
- Treatment with drugs that have a high incidence of diarrhea
- Drugs which act primarily in the GI tract (e.g. Orlistat, acarbose)
- Chronic systemic steroid treatment or systemic steroids for > 7 consecutive days for worsening of an underlying condition within 4 weeks of screening. Use of topical or inhaled steroids is permitted
- Use of other investigational drugs at the time of enrollment, or within 30 days or 5 half-lives of enrollment, or longer if required by local regulations, and for any other limitation of participation in an investigational trial based on local regulations
- Unless allowed by the study protocol, use of any other prescription drugs, new herbal supplements, within four (4) weeks prior to initial dosing, and/or over-the-counter (OTC) medication, new dietary supplements (vitamins included), within 3 days prior to initial dosing.

Subjects may need to discontinue the study treatment if treated with any of the prohibited medications during the study. Concomitant and prior medications (dose, regimen, indication and treatment duration) must be recorded in the CRF.

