6.8 Recommended treatment of adverse events

Based on prior clinical experience with LIK066, which was administered to more than 200 subjects at doses up to 350 mg single dose or up to 150 mg for 12 weeks, LIK066-related AEs can be managed by clinical monitoring including vital signs and blood tests. If diarrhea occurs, it can be treated with oral rehydration therapy if needed. More aggressive treatment, if required, will be performed at the discretion and direction of the investigator, with timely communication with the sponsor. Stopping rules ([Section 7.4](#)) will be applied as appropriate. Medication used to treat AEs must be recorded on the Concomitant medications/Significant non-drug therapies CRF.

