6.9 Rescue medication

This is not a therapeutic study; therefore, rescue medication use is not applicable.

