6.10 Concomitant treatment

Except for medication which may be required to treat adverse events, no medication including OTCs other than study drugs will be allowed from the first dosing until all of the Study Completion evaluations have been conducted. If needed, acetaminophen or ibuprofen is acceptable for incidental and limited use. Aspirin, antihypertensive, dyslipidemia, COPD and GERD medications are allowed but subjects must be on a stable regimen for 12 weeks or more prior to randomization.

The investigator must instruct the subject to notify the study site about any new medications he/she takes after the subject was enrolled into the study.

All prescription medications, over-the-counter drugs and significant non-drug therapies (including physical therapy and blood transfusions) administered or taken within the timeframe defined in the entry criteria prior to the start of the study and during the study, must be recorded on the Concomitant medications/Significant non-drug therapies CRF.

Medication entries should be specific to trade name, the single dose and unit, the frequency and route of administration, the start and discontinuation date and the reason for therapy.

Each concomitant drug must be individually assessed against all exclusion criteria/prohibited medication. If in doubt, the investigator should contact Novartis before randomizing a subject or, if the subject is already enrolled, to determine if the subject should continue participation in the study.

7 Study completion and discontinuation

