7.2 Discontinuation of study treatment

Discontinuation of study treatment for a subject occurs when study treatment is stopped earlier than the protocol planned duration. Discontinuation of study treatment can be decided by either the subject or the investigator.

Study treatment must be discontinued under the following circumstances:

[figure not shown]
- Subject decision - subjects may choose to discontinue study treatment for any reason at any time.
- The investigator believes that continuation would negatively impact the safety of the subject or the risk/benefit ratio of trial participation.
- Any protocol deviation that results in a significant risk to the subject's safety.
- Pregnancy
- Use of prohibited treatments.

Study treatment of individual subject will be discontinued when that subject experiences:

- Clinically significant diarrhea, suspected to be related to the study drug, that may put the subject at risk at the discretion of the investigator and in consultation with the sponsor
- Clinically significant symptomatic orthostasis confirmed by repeated orthostatic blood pressure changes (more than a 20 mmHg drop in systolic or 10 mmHg drop in diastolic blood pressure and increase in heart rate >20 bpm (compared to the sitting results) when blood pressure and pulse are taken after at least 3 minutes standing)
- Clinically significant urinary tract or genitourinary infections, at the discretion of the investigator and in consultation with the sponsor if deemed necessary.
- Clinically symptomatic hypoglycemia confirmed by repeated blood glucose levels (<56 mg/dL).
- Ketoacidosis (symptoms of ketoacidosis include nausea, vomiting, abdominal pain, unusual tiredness and trouble breathing) confirmed by blood pH and ketones bodies in both plasma and urine.
- Any laboratory abnormalities that in the judgment of the investigator, taking into consideration the subject's overall status, prevents the subject from continuing participation in the study.
- Any hospitalization, or other SAE, that is suspected to be related to the study treatment.

If discontinuation of study treatment occurs, the investigator must determine the primary reason for the subject's premature discontinuation of study treatment and record this information on the Dosage Administration CRF.

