COMD01	Subject received prohibited concomitant medication	

Summary of frequency of subjects in each analysis set will be provided and subjects excluded from each analysis set will be listed with reasons being excluded. All protocol deviation will be listed together with corresponding analysis set(s) being excluded when applicable.

If updates to this table are needed, an amendment to the SAP needs to be implemented prior to DBL.

6 Statistical methods for Pharmacodynamic (PD) parameters

All subjects within the PD analysis set will be included in the PD data analysis.

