6.1.3.1 Model checking procedures

Missing data will be assumed to be missing at random and thus the above analysis will be performed on all available data. There will be no imputation of missing data.

The interaction between treatment and day will be assessed, and if non-significant, the results from the 3 days will be averaged and corresponding model-based quantities extracted.

The model assumption of negative binomial distribution will be examined, especially if over-dispersion (i.e. variance>mean) exist. If the data doesn't fit negative binomial distribution or over-dispersion doesn't exist, other models such as Poisson regression will be explored.

The model assumption of no first-order carry-over effect may be evaluated by incorporating first-order carry-over effects into the above statistical models, and performing a type 3 test for the first order carry-over effect. In addition, descriptive summary statistics will also be provided by treatment sequence and visit in order to assess carry-over effect.

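### Medication given for study diarrhea can be classed as permitted AE treatment or as a prohibited drug, and the prohibited reading removes the subject from the primary analysis because of the primary outcome

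*Protocol*

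**What the plan says.** **Status of the medication.** Protocol 5.2 begins "Except for medication which may be required to treat adverse events, no medication including OTCs other than study drugs will be allowed", and 6.10 repeats the allowance. Section 6.8 names oral rehydration for diarrhea and adds "More aggressive treatment, if required, will be performed at the discretion and direction of the investigator", in communication with the sponsor. The prohibited list in 5.2 includes "Drugs which act primarily in the GI tract (e.g. Orlistat, acarbose") and carries no adverse-event exception. Section 6.10 adds: "Each concomitant drug must be individually assessed against all exclusion criteria/prohibited medication".

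**Consequence for the subject.** Section 5.2 treats stopping study treatment after a prohibited medication as a possibility. Section 7.2 lists "Use of prohibited treatments" among the circumstances in which stopping is mandatory.

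**Consequence for the analysis.** SAP Section 4, Table 4-1, lists COMD01 ("Subject received prohibited concomitant medication") under deviations that exclude the subject from the PD analysis set, which is the set used for the primary analysis. The table limits exclusion to the affected periods for TRT01 only. For subjects who stay in, SAP 6.1.3.1 says "Missing data will be assumed to be missing at random and thus the above analysis will be performed on all available data", with no imputation. Neither document says how stool counts after treatment of diarrhea are to be handled.

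**The concern.** The primary variable is the daily number of stools with a Bristol score of 6 or 7, and diarrhea is also the expected adverse event. Any medication given for it is therefore prompted by the outcome and may change the outcome. Whoever decides to treat knows the assigned meal or supplement, because the trial is open label.

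Two defensible readings of the protocol give two different primary data sets from the same event. In one, suppressed counts are analysed as if untreated. In the other, a subject is deleted because the diarrhea was bad enough to treat. With power resting on 5 completers in each of 3 sequences (15 per part), a few exclusions matter. If the classification is left until the data are visible, the choice itself can depend on the results.

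**Working it through.** **1. The two readings side by side**

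| Step | Permitted AE treatment | Prohibited GI-acting drug |
|---|---|---|
| Source | 5.2 opening, 6.8, 6.10 | 5.2 list, 6.10 drug-by-drug check |
| Study treatment | continues unless another rule stops it | possible stop (5.2) or mandatory stop (7.2) |
| Primary analysis | counts kept at face value | COMD01: whole subject out of the PD set |

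No sentence ranks one column above the other. There is also a third route. Sections 6.5 and 7.2 stop study treatment for intolerance or clinically significant diarrhea, which leaves on-treatment days missing.

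**2. The plan's own figures (Protocol 11.7)**

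- Enrolment: 30 / (1 − 0.375) = 48 and 5 / (1 − 0.375) = 8 per sequence. Both reproduce.
- Power: Poisson counts with a shared gamma subject effect, one observation per period, 3 × 5 subjects. With a negative binomial mixed model, power is 0.81 to 0.88 at two-sided alpha 0.20, 0.71 to 0.80 at 0.10 and 0.58 to 0.66 at 0.05. The plan states no alpha. Its figure of at least 80% is matched at 0.20, the level implied by its 80% intervals.

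**3. Size of the shift in that model**

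Assumptions not in the documents: medication is given when a daily count reaches T (6 to 12), and it halves that count.

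*Counted while treated, hand check at dispersion 1.* Counts are then geometric, so P(Y ≥ T) = (m/(1+m))^T, and the treated mean is m − 0.5 × P × (T + m).

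- T = 12, m = 3: 0.75^12 = 0.0317; 3 − 0.5 × 0.0317 × 15 = 2.762.
- T = 12, m = 1.5: 0.6^12 = 0.00218; 1.5 − 0.5 × 0.00218 × 13.5 = 1.485. Ratio 1.485/2.762 = 0.54.
- T = 6, m = 3: 0.75^6 = 0.178; 3 − 0.5 × 0.178 × 9 = 2.199.
- T = 6, m = 1.5: 0.6^6 = 0.0467; 1.5 − 0.5 × 0.0467 × 7.5 = 1.325. Ratio 1.325/2.199 = 0.60.

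*Simulation over both planning dispersions (2.4 and 1), 2 million subjects per cell:*

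| Planning means per day | Untreated ratio, difference | Counted while treated | Subject removed |
|---|---|---|---|
| 3 vs 1.5 | 0.50, 1.5 | 0.54–0.60, 0.82–1.28 | 0.52–0.57, 0.49–1.26 |
| 5 vs 3 | 0.60, 2.0 | 0.67–0.70, 1.00–1.30 | 0.63–0.68, 0.40–1.27 |

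Power at two-sided 0.20, 5 per sequence, T = 8 or 12 (Poisson mixed model, 250 trials per cell): 0.62 to 0.87 if counted and 0.34 to 0.87 if removed, against 0.86 to 0.90 with no treatment.

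**4. A case in the other direction**

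Suppose the most affected 15% of subjects get no benefit and the rest have a ratio of 0.4. The overall ratio is then 0.66 to 0.76. It moves away from 1, to 0.62–0.71 if treated days are counted and 0.47–0.58 if subjects are removed.

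**The case against.** The adverse-event allowance opens 5.2 and is repeated in 6.10, so it is reasonable to read it as governing the list below it. The investigator is also told to communicate with the sponsor (6.8) and to ask when in doubt (6.10). Oral rehydration, the only treatment named for diarrhea, is not evidently a prohibited GI-acting drug, and no antidiarrheal is named anywhere. Protocol 1.3.1 reports no withdrawals for adverse events related to LIK066, and the planning counts come from 50 mg three times daily rather than once daily. Treatment beyond rehydration may therefore be rare, and the study is declared non-confirmatory.

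These points limit the frequency and the size. They do not supply an analysis rule: asking the sponsor settles whether a subject continues, not whether COMD01 applies or how treated counts are used.

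Three stronger readings are tempting but are not supported:

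- *That both routes must understate the benefit.* This follows under the single multiplicative effect of 11.7. Step 4 shows it can reverse. Removal also takes out all of a subject's periods, so the ratio shifts less than the absolute difference and much of the loss is power.
- *That different sites would classify the same event differently.* The documents do not establish more than one site. The ambiguity exists within one site.
- *That 6.9 contradicts the adverse-event allowance.* Its statement, "This is not a therapeutic study; therefore, rescue medication use is not applicable", concerns rescue in a therapeutic sense and can stand beside adverse-event treatment.

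**Conclusion.** The point holds. The protocol gives medication for study diarrhea beyond rehydration two possible statuses, and it conflicts with itself on the consequence of a prohibited drug. Applied as written under the second status, COMD01 is an exclusion caused by the primary outcome.

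In the planning model, with the assumed triggers and halving, the ratio moves toward 1 by about 0.02 to 0.10 and the absolute difference falls by about 15% (1.5 to 1.28) to 80% (2.0 to 0.40). Power can fall well below the planned 80%, most of all under exclusion. The direction is conditional on a common multiplicative effect. The size is illustrative because the documents give no treatment frequency, and with no such treatment there is no effect at all. The case for a rule fixed in advance rests on the conflict in the text and the outcome-driven exclusion, not on any one of these figures.

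**What to change.** **Protocol.** The sponsor should reconcile 5.2, 6.8, 6.10 and 7.2 so that medication given for study diarrhea has one status and one stated consequence. Which medication is allowed is for the sponsor to settle.

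**SAP, by amendment before database lock** (the route that SAP Section 4 itself requires for changes to Table 4-1):

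1. Whatever that status, do not use COMD01 to drop a subject from the primary analysis solely because medication was given to treat diarrhea as an adverse event. Keep the as-observed counts as primary.
2. Add a pre-specified sensitivity analysis of treated days, for example setting counts after the first such dose in that period to missing. State that it relies on missing at random and itself removes days from the worst-affected subjects.
3. Tabulate subjects and days with diarrhea treatment, and discontinuations for diarrhea, by treatment and period.

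**Cost.** A protocol clarification, one sensitivity analysis and one table. Concomitant medication, with dates and reason, is already collected on the CRF. The downside is that some subjects with treated counts stay in the primary set, so that analysis describes diarrhea with any treatment given, not untreated diarrhea.
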